Study Protocol and Statistical Analysis Plan

Study Title: Musculoskeletal Plasticity After Spinal Cord Injury

NCT02622295

Document Version: 8/25/2022

Study Objectives

Patients with spinal cord injury (SCI) experience metabolic syndrome, diabetes, obesity, pressure ulcers, and cardiovascular disease at far greater rates than the general population. A rehabilitation method to prevent or reverse the systemic metabolic consequences of SCI is a pressing need.

The **purpose** of this study is to determine the dose of muscle activity that can enhance an oxidative muscle phenotype and improve clinical markers of metabolic health and bone turnover in patients with SCI. The **long-term goal** of this research is to develop exercise-based interventions to prevent secondary health conditions such as diabetes and to ultimately protect health-related quality of life (QOL).

Specific Aim 1: To compare changes in skeletal muscle gene regulation in individuals who receive high frequency (HF) active-resisted stance and low frequency (LF) active-resisted stance for 3 years.

Hypothesis 1: The expression of genes regulating skeletal muscle metabolism will support that HF and LF both instigate a shift toward an oxidative muscle phenotype. A novel finding will be that LF is a powerful regulator of oxidative pathways in skeletal muscle.

Specific Aim 2: To compare changes in systemic markers of metabolic health and bone turnover in individuals with SCI who receive HF or LF for 3 years.

Hypothesis 2: HF and LF will both reduce glucose/insulin levels and HOMA (homeostasis model assessment) score.

Secondary Aim: To measure subject-reported QOL using the EQ-5D survey metric.

Hypothesis 3: HF and LF subjects will show a trend toward improved self-reported QOL after 3 years. There will be an association between metabolic improvement and improved perception of QOL. These observations will support that this intervention has strong feasibility for future clinical translation.

Design

Population: Individuals with motor-complete spinal cord injury (SCI) (AIS A – B), 21 to 60 years of age.

Exclusion Criteria: Pressure ulcers, chronic infection, lower extremity muscle contractures, deep vein thrombosis, bleeding disorder, recent limb fractures, any comorbid disease known to affect bone metabolism (such as parathyroid dysfunction), pregnancy, anti-osteoporosis medications, Vitamin D supplements, Metformin or other medications for diabetes

Enrollment: Non-random assignment

Study Arm 1: Acute gene regulation in response to single-session electrically induced exercise

Study Arm 2: Adaptations in gene regulation, metabolic markers, and subject-report metrics in response to up to 3 years of electrically induced exercise

Methods

Baseline Characteristics: Participants will provide information on age, sex, race, ethnicity, and level of SCI (quadriplegia, paraplegia)

Study Arm 1: Participants will undergo unilateral vastus lateralis skeletal muscle biopsy: they will be positioned in supine, the skin over the biopsy site will be sterilized, up to 3 mL of 1% lidocaine will be injected locally, and a 1/8th inch incision will be made with a scalpel. The biopsy needle will then be inserted and four cores of muscle (~ 20 mg) will be obtained from four passes of the needle through the same puncture site. The incision site will be closed with steri-strips or a butterfly bandage and the subject will be told not to perform electrical muscle stimulation or wet the area for 48 hours. Muscle specimens will be immediately processed for microarray analysis. Participants will then undergo a single session of electrically-induced exercise to the quadriceps and hamstrings muscles of the non-biopsied limb. Stimulating electrodes will be placed over the quadriceps and hamstrings muscles, and electrical stimulation will be given to induce an isometric closed kinetic chain knee extension moment. Participants will rest for 3 hours and then the vastus lateralis biopsy procedure will be repeated on the limb that performed electrically-induced exercise.

Study Arm 2: Participants will complete a baseline assessment including the biopsy procedure described above, completion of the EQ-5D self-reported quality of life survey, and venipuncture. Venous blood will be collected into vacutainer tubes with anticoagulant for glucose, kept on ice in dark conditions. The blood will be centrifuged and analyzed with a blood auto-analyzer. A portion of the blood sample will be tested via enzyme-linked immunosorbent assay (ELISA). Insulin and glucose values will be entered into the homeostasis model assessment equation (HOMA) to yield a HOMA score. After two weeks, participants will begin electrically induced exercise training. They will perform electrically induced exercise as described above for up to 3 years. At the conclusion of training, participants will undergo repeat biopsy, EQ-5D survey, and venipuncture.

Outcome Measures: Microarray will be used to measure mRNA transcription levels for genes that regulate muscle atrophy (myostatin – MSTN), cellular adaptation to exercise (peroxisome proliferator-

activated receptor gamma coactivator alpha – PGC1-alpha), and muscle oxidative metabolism (pyruvate dehydrogenase kinase – PDK4, and succinate dehydrogenase-B – SDHB). Standard clinical assays will be used to measure levels of serum biomarkers for metabolism (fasting insulin, fasting glucose). Fasting insulin and fasting glucose will be used to calculate HOMA-IR, an index of insulin resistance. ELISA will be used to measure levels of osteocalcin, a biomarker of bone turnover. For the EQ-5D metric of health-related quality of life, self-reported numeric health state will be converted to Quality-Adjusted Life Years (QALY) using standardized tables.

Statistical Analysis Plan

Gene mRNA transcript levels will be expressed as Log_2 intensity (arbitrary units). Each blood biomarker will be expressed as its commonly-used clinical unit of measure (eg. mg/dL). EQ-5D health states will be expressed as QALY.

Change over time for each outcome measure will be assessed via repeated-measures one-way ANOVA. For study Arm 1, gene expression levels from the baseline biopsy will be contrasted to the 3 hour post-exercise biopsy. For study Arm 2, post-training values for all outcome measures will be contrasted to the baseline assessment point.

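### Hypothesis 1 speaks of oxidative pathways, but the SAP tests four named transcripts one at a time, with no variance borrowing across the array and no rule linking the results to the pathway claim

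*Combined protocol and SAP*

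**What the plan says.** Study Objectives, Hypothesis 1, makes two statements. The first is about genes and phenotype: "The expression of genes regulating skeletal muscle metabolism will support that HF and LF both instigate a shift toward an oxidative muscle phenotype". The second is about pathways and about LF alone, and predicts as a new result that "LF is a powerful regulator of oxidative pathways in skeletal muscle".

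Under Methods, the biopsy cores go onto arrays: "Muscle specimens will be immediately processed for microarray analysis". The platform and its gene content are not given.

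Outcome Measures lists four transcripts, each with a function. MSTN is listed under atrophy and PGC1-alpha under exercise adaptation ("Microarray will be used to measure mRNA transcription levels for genes that regulate muscle atrophy (myostatin – MSTN), cellular adaptation to exercise"). The other two come under "muscle oxidative metabolism (pyruvate dehydrogenase kinase – PDK4, and succinate dehydrogenase-B – SDHB".

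The Statistical Analysis Plan puts transcripts on the log2 scale and gives one method: "Change over time for each outcome measure will be assessed via repeated-measures one-way ANOVA". The contrasts are baseline against 3 hours after exercise in Arm 1, and baseline against post-training in Arm 2. There is no composite, no gene-set test, no expected direction per gene and no analysis by stimulation frequency.

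**The concern.** The claim and the test are at different levels. The second sentence of Hypothesis 1 is about pathways; the analysis yields four separate gene results, two of them for genes that the plan itself labels oxidative. If PDK4 changed and SDHB did not, or if they moved in opposite directions, the SAP would not say whether the hypothesis was supported. That judgement would be made after the data were seen.

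The second issue is efficiency. A paired t-test estimates each gene's variance from that gene's own few pairs. If the array carries many transcripts, the rest of the array tells us what a typical variance is, and the plan leaves that information unused. Each pair costs two invasive biopsies, in Arm 2 up to 3 years apart, so a gain that needs no new sample deserves consideration.

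**Working it through.** The documents state no sample size, SD, effect size or alpha for this analysis, so there is no planned figure to reproduce. Everything from step 3 on is an illustration on assumed inputs.

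**1. Count.** Named transcripts: 4. Labelled oxidative metabolism: 2 (PDK4, SDHB). Tests planned on more than one gene: 0.

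**2. What the planned test is.** With two time points, the repeated-measures ANOVA has F on 1 and n − 1 df, and F = t² for the paired t. At 8 pairs that is 7 df.

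**3. Moderated paired t.** With prior df d0 and prior variance s0² taken from all probes:

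- moderated variance = (d0·s0² + (n − 1)·s²) / (d0 + n − 1)
- t = mean log2 change / √(moderated variance / n), on d0 + n − 1 df

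At 8 pairs the df rise from 7 to 3 + 7 = 10 (d0 = 3) or 6 + 7 = 13 (d0 = 6). In the simulation, gene variances were d0·s0²/χ² with d0 df, the prior was treated as known, and the two-sided level was 5%. Results at 8 pairs:

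| True change | d0 | Paired t | Moderated t |
|---|---|---|---|
| none | 3 and 6 | 5% | 5% |
| 1 × s0 | 3 | 57% | 62% |
| 1 × s0 | 6 | 62% | 70% |
| 1 × gene's own SD | 3 | 68% | 72% |
| 1 × gene's own SD | 6 | 68% | 74% |

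The gains are 5, 8, 4 and 6 points. The same simulation at 20 pairs gives gains of under 2 points on the s0 scale and almost none on the own-SD scale, in part because power is already high there.

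**4. Gene-set mean.** Take a 30-gene set in which a fraction f of the genes shifts by 0.5 SD in one direction, with equal between-gene correlation ρ. The standardised effect of the mean is 0.5·f / √(ρ + (1 − ρ)/30). For f = 1:

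- ρ = 0.1: 0.5/√0.130 = 1.39
- ρ = 0.3: 0.5/√0.323 = 0.88
- ρ = 0.6: 0.5/√0.613 = 0.64

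For f = 0.5 these halve to 0.69, 0.44 and 0.32. Power from the noncentral t on n − 1 df, two-sided 5%:

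| Pairs | One gene shifting 0.5 SD | Set, all shift (ρ 0.1 / 0.3 / 0.6) | Set, half shift (ρ 0.1 / 0.3 / 0.6) |
|---|---|---|---|
| 12 | 35% | 99 / 79 / 52% | 59 / 29 / 17% |
| 8 | 23% | 92 / 57 / 35% | 40 / 19 / 12% |

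The all-shift column is a best case. With half the set moving, the set test beats one responsive gene only at ρ = 0.1. Changes in opposite directions would cancel in the mean and lower power further.

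**5. Which groups the tests compare.** Arm 1 is a single session and Arm 2 is training for up to 3 years. Neither arm is LF or HF. A set test run once per study arm would therefore not address a statement about LF.

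**The case against.** A short list of marker genes fixed in advance is a legitimate design. It limits multiplicity and selective reporting, and the first sentence of Hypothesis 1 rests on expression of metabolic genes, so the authors may intend all four, PGC1-alpha included, as pathway markers. This stands. The four tests are valid for those genes, and narrowing the wording of the hypothesis would close the gap at no cost. What it leaves open is how the four results are to be read together, because the SAP gives neither directions nor a rule.

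The moderated t can also be called a preference rather than the repair of a defect. That is fair: its gain is modest and depends on the assumed prior.

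Two stronger readings are tempting. A reader might infer that the plan throws away pathway data known to be on the arrays. The documents do not give the array's content, so they support only the statement that no analysis of any other transcript is planned. A reader might also infer that a gene-set test should decide Hypothesis 1 because it is far more powerful. The documents give no direction or co-movement of genes from which to expect that, and step 4 shows that the advantage can reverse.

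**Conclusion.** The gap between hypothesis and analysis is real on the text: a pathway claim, four single-gene tests, two of them on genes labelled oxidative, and no link between the results and the claim. It limits what may be concluded; it does not invalidate the four tests.

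The dependable analytic improvement is the moderated paired t: about 4 to 8 points of power at 8 pairs with the error rate held at 5%, and little by 20 pairs. This rests on an assumed effect of 1 SD, prior df of 3 to 6, and an array with enough transcripts to estimate the prior variance well. A gene-set test can support the pathway statement but should not decide it. Unless it is run within the LF group, it would not bear on the sentence about LF at all.

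**What to change.** 1. In the Statistical Analysis Plan, replace the ANOVA for the four named genes with an empirical-Bayes moderated paired t-test, with the prior variance estimated from all probes on the array. Report fold change, 2 to the power of the mean log2 change, with its 95% CI. State the platform and the number of transcripts.
2. Then do one of the following:
   - limit the Hypothesis 1 conclusion to the four named genes; or
   - add an oxidative-metabolism gene set, fixed with expected directions before the arrays are analysed, and test it in Arm 2 separately for the HF and LF groups, not pooled per study arm. Present it as supporting evidence, and label it post hoc if the arrays have already been analysed.

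The cost is a little more analysis work, with no new samples or assays. Item 1 and the gene-set option apply only if the array carries enough transcripts. If it does not, keep the paired test, report the fold changes with intervals, and narrow the hypothesis.

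### Aims 1 and 2 compare HF with LF between people, but the plan describes neither a random route to a frequency nor any adjustment, so an HF-LF difference could not be separated from who received which

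*Combined protocol and SAP*

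**What the plan says.** Study Objectives gives the purpose as to "determine the dose of muscle activity that can enhance an oxidative muscle phenotype". Two aims then set a contrast between frequencies. Specific Aim 1 is "To compare changes in skeletal muscle gene regulation in individuals who receive high frequency (HF) active-resisted stance and low frequency (LF) active-resisted stance for"; the stated period is 3 years. Specific Aim 2 is "To compare changes in systemic markers of metabolic health and bone turnover in individuals with SCI who receive HF or LF for 3 years". Hypothesis 3 says that "HF and LF subjects will show a trend toward improved self-reported QOL after 3 years", which treats HF and LF as separate sets of people.

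The Design section has one line on assignment: "Enrollment: Non-random assignment". The two arms follow at once, and neither is defined by frequency. The first is "Study Arm 1: Acute gene regulation in response to single-session electrically induced exercise". The second concerns adaptations "in response to up to 3 years of electrically induced exercise". HF and LF are not mentioned again after Hypothesis 3.

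Under Methods, the baseline characteristics are demographic items and injury level in two categories, quadriplegia or paraplegia. The Statistical Analysis Plan tests change over time with a one-way repeated-measures ANOVA and contrasts post-training with baseline in Arm 2. It names no covariate and no HF-LF term.

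**The concern.** The question of dose rests on a contrast between different people. If frequency is not given at random, those who receive HF may differ from those who receive LF in ways that also bear on how gene expression, glucose, insulin and osteocalcin change over the training period. An HF-LF difference, or the lack of one, would then have more than one explanation.

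This is not the same gap as the missing HF-LF test in the Statistical Analysis Plan. Adding such a test would supply a p-value, but its meaning would still depend on how the two groups came about, which the plan does not say. At stake is whether Aims 1 and 2 can be answered as comparisons between doses.

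**Working it through.** The plan gives no figure to reproduce: no sample size, allocation ratio, effect size, standard deviation, power or dropout rate. The check is therefore mainly one of reading and logic.

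**Step 1. The relevant statements side by side.**

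| Element | What the plan gives |
|---|---|
| Contrast in Aims 1 and 2 | HF versus LF, between individuals |
| Named arms | Single session versus training; neither defined by frequency |
| Assignment | Non-random; no rule, chooser or criterion |
| Route to HF or LF | Not described |
| Matching, stratification, adjustment | None |
| Baseline variables | Demographics and injury level; no stated use in the analysis |
| Planned Arm 2 contrast | Post-training versus baseline |

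**Step 2. What an HF-LF difference in change would contain.** Write it as the sum of two terms:

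- dose term: mean change under HF minus mean change under LF, in the same people;
- selection term: mean change that the HF people would have shown under LF, minus mean change that the LF people show under LF.

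Random allocation makes the selection term zero on average. Without it, nothing in the plan sets the term to zero or estimates it. Analysing change from baseline removes stable differences in level, but not differences in expected change. Those could relate to baseline value, injury level or length of training, which Arm 2 allows to vary up to 3 years.

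**Step 3. Which contrasts are touched.** Each planned contrast in the Statistical Analysis Plan compares a participant with himself or herself, so the selection term does not enter. It enters only the between-person comparison that Aims 1 and 2 call for.

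**Step 4. Illustration only; every input is an assumption.** Suppose the groups differ by 20 to 40 percentage points in one trait, and the trait shifts the change by 0.3 to 0.6 SD. Then bias = imbalance × shift:

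- 0.2 × 0.3 = 0.06 SD
- 0.2 × 0.6 = 0.12 SD
- 0.4 × 0.3 = 0.12 SD
- 0.4 × 0.6 = 0.24 SD

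For a bias b of 0.2 SD with no true HF-LF difference, n per group, two-sided alpha 0.05 and a normal approximation, the chance of a false difference is Φ(b/√(2/n) − 1.96) + Φ(−b/√(2/n) − 1.96):

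| n per group | b/√(2/n) | Chance at b = 0.2 SD | Chance at b = 0 |
|---|---|---|---|
| 10 | 0.447 | 7% | 5% |
| 20 | 0.632 | 10% | 5% |
| 40 | 0.894 | 15% | 5% |

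A larger sample does not remove the bias; it makes a false difference more likely. Several traits may add up or cancel.

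**The case against.** The strongest objection concerns what the assignment line refers to. It is followed immediately by the acute and training arms, the only arms that the Design section names, so its natural reading is entry to those arms. A reader might infer that the plan declares HF versus LF to be non-random. The documents do not support that: they are silent on how frequency is given. Nor do they state or exclude a reason for choosing a frequency, and they do not say that staff or participants match frequency to any trait. This part of the objection stands. It does not close the gap, because no other statement offers a random route to HF or LF.

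A second objection is that the hypotheses do not need the comparison. Hypotheses 1 and 2 expect both frequencies to produce change, Hypothesis 3 expects improvement in both, and the planned tests are within-person. This is correct as far as it goes, and those tests are untouched. Aims 1 and 2 nevertheless say that changes will be compared, and the purpose is framed as finding a dose.

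A third objection is that non-random assignment is openly declared. That makes it a limit on inference and not a contradiction. The plan still does nothing to handle the limit.

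Finally, a reader might think that randomising HF against LF would also secure the expected finding that LF strongly regulates oxidative pathways. If that finding is read as change within LF, it would not. Natural course over the training period would remain a rival explanation, since the plan has no untreated group.

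**Conclusion.** The concern holds in a limited form. The aims call for an HF-LF comparison between people, and the plan describes neither random allocation to frequency nor any adjustment. Following the plan as written, an HF-LF difference could not be attributed to dose as distinct from differences between the groups.

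The conclusion rests on two readings: that HF and LF are separate groups, as Aims 1 and 2 and Hypothesis 3 imply, and that the absence of a described random route means none is planned. If frequency is in fact randomised, one added sentence would settle the matter.

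The size and direction of any bias are unknown. The range of 0.06 to 0.24 SD per trait shows how such a bias behaves and is not an estimate for this study. It would be wrong to infer that the pre-post results are biased by HF-LF selection, or that bias is certain to be present.

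**What to change.** State in the protocol how a participant comes to receive HF or LF, and whether the assignment line refers to arm, frequency or both.

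In the Statistical Analysis Plan, add an HF-LF comparison within Arm 2: ANCOVA of the post-training value on frequency group, baseline value and injury level. Report it as non-randomised. Acknowledge residual confounding by traits not listed at baseline, such as time since injury, which this model cannot remove. This uses only data already collected and costs a few sentences.

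If Arm 2 is still recruiting, which the documents do not say, allocate further entrants to HF or LF from a concealed 1:1 list in random blocks, stratified by injury level. Entry to Arm 1 or Arm 2 can stay non-random. Participants allocated before the list came into use should be identified as such in the report. The cost is preparing the list and losing free choice of frequency; no extra participants, visits or procedures are needed.

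### The EQ-5D value at each visit is labelled a QALY, but the described table look-up has no time term and yields a utility

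*Combined protocol and SAP*

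**What the plan says.** The Secondary Aim under Study Objectives is "To measure subject-reported QOL using the EQ-5D survey metric"; no other instrument is named for it. Hypothesis 3 expects a trend to better self-reported quality of life after 3 years and an association with metabolic improvement.

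Outcome Measures defines the endpoint: the "self-reported numeric health state will be converted to Quality-Adjusted Life Years (QALY) using standardized tables". The Statistical Analysis Plan repeats the unit: "EQ-5D health states will be expressed as QALY".

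Under Methods, Study Arm 2, the survey is given twice. The baseline assessment includes "completion of the EQ-5D self-reported quality of life survey". Then: "After two weeks, participants will begin electrically induced exercise training". Next: "They will perform electrically induced exercise as described above for up to 3 years". Finally: "At the conclusion of training, participants will undergo repeat biopsy, EQ-5D survey, and venipuncture".

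The analysis is a repeated-measures one-way ANOVA, with this contrast: "For study Arm 2, post-training values for all outcome measures will be contrasted to the baseline assessment point".

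The document gives no time horizon, multiplication by duration, area-under-the-curve step or one-year convention for the EQ-5D. It does not use the terms utility or index value, and it does not name the EQ-5D version or the tables.

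**The concern.** A QALY combines two things: how good a health state is (the utility) and how long it lasts. The plan uses only the first and gives it the name of the product. The label stands in both the outcome definition and the reporting rule, so it is not a stray word.

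Hypothesis 3 asks whether quality of life is better at the end of training than at the start. A utility difference answers that directly. Followed as written, however, the plan would report a change in QALYs, a quantity it never estimates. A reader of a study with up to 3 years of training could take that figure as life-years gained, or carry it into a health-economic comparison as a benefit estimate.

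**Working it through.** The plan states no EQ-5D value or QALY figure, so there is nothing to reproduce. The check is one of dimensions, followed by an illustration of how far the two quantities can differ.

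**1. What the described step produces.** Input: a health state at one visit. Operation: table look-up. Output: a table value, u. Time does not enter, so u is a utility. Accumulated QALYs would be u integrated over the interval; with two visits T years apart and a straight line between them, T × (u0 + u1)/2.

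**2. What the planned contrast needs.** It needs one value per participant at baseline and one after training. No follow-up time has accrued at baseline, whereas accumulated QALYs are a single value per participant over the whole interval. Only a per-visit quantity fits the contrast, so the result is D = u1 − u0.

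**3. Longest interval between surveys.** From Methods, Study Arm 2: two weeks, then up to 3 years of training.

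T = 3 + 14/365.25 = 3.04 years.

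**4. QALY gain against a constant baseline utility.** No value of D is assumed. The comparator and the paths are assumptions for illustration; the plan specifies neither.

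| Path of utility between surveys | Formula | Result at T = 3.04 |
|---|---|---|
| All change at the end | 0 | 0 |
| Linear | D × T/2 | 1.52 × D |
| All change at the start | D × T | 3.04 × D |
| Planned contrast, for comparison | D | D (any T) |

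**5. Dependence on duration.** Take assumed utilities u0 = 0.50 and u1 = 0.60, so D = 0.10. The planned contrast gives 0.10 for every training length. The linear-path gain, 0.10 × T/2, is:

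| T (years) | Gain (QALYs) |
|---|---|
| 0.5 | 0.025 |
| 1 | 0.05 |
| 2 | 0.10 |
| 3 | 0.15 |

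On this path the two agree only at T = 2. Because training lasts up to 3 years and may differ between participants, no single multiplier need convert the reported figure into QALYs for everyone.

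**6. Effect on the test.** The ANOVA runs on the table values whatever they are called. Renaming the unit leaves every value, the F statistic and the p-value unchanged.

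**The case against.** The strongest reply is that the label is shorthand. If the tables express each state's value per year lived in it, the number is the same and the fault is an unstated convention. The tables are not named, so what they are scaled to cannot be read from the document, and that EQ-5D tables give a utility is standard methodology that the plan does not itself state. Moreover, no planned result changes, the plan makes no claim about QALYs gained or cost-effectiveness, and a multiplier between 0 and 3.04 on an unknown D shows only that two quantities differ by definition.

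Much of this stands. The identification of the value as a utility is inferred from the operation described. The test is unaffected, the misreading is a risk in reporting and not a stated intention, and the multipliers do not measure an error in this trial. What does not stand is the per-year rescue: the plan states no such convention and spells the term out as life-years. Nor does an accumulated-QALY reading fit, because the contrast needs a baseline value.

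**Conclusion.** The concern holds. As written, the unit of the only measure named for the Secondary Aim is wrong in both its definition and its reporting rule; the quantity the plan would analyse is a change in EQ-5D utility. The fault is confined to labelling and interpretation, and no numerical bias in the planned contrast is claimed. The conclusion rests on the look-up being used as described, with no time term. The illustrative multipliers also rest on a constant-baseline comparator and assumed utility paths. This should be corrected before the outcome is reported.

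**What to change.** In the EQ-5D sentence of Outcome Measures and the matching sentence of the Statistical Analysis Plan, replace QALY with EQ-5D index value (utility). Report the Arm 2 post-training minus baseline change in index units, and do not describe it as QALYs gained. In the same edit, name the EQ-5D version and the value set behind the tables so that the index can be reproduced.

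The cost is wording in two sentences, with no new data and no change to the model or contrast. If the investigators do intend QALYs, relabelling is not enough: they would need to define a time horizon, an area-under-the-curve calculation and the handling of unequal training lengths, and analyse one value per participant in place of the baseline contrast. Neither the Secondary Aim nor Hypothesis 3 requires that.

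### Aims 1 and 2 promise an HF versus LF comparison of change, but Arm 2 identifies no HF or LF group and the SAP's only test is of time.

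*Combined protocol and SAP*

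**What the plan says.** **Study Objectives.** The purpose is "to determine the dose of muscle activity that can enhance an oxidative muscle phenotype". Specific Aim 1, covering 3 years of training, is "To compare changes in skeletal muscle gene regulation in individuals who receive high frequency (HF) active-resisted stance and low frequency (LF"). Specific Aim 2 is "To compare changes in systemic markers of metabolic health and bone turnover in individuals with SCI who receive HF or LF for 3 years". Of the hypotheses, the second states that "HF and LF will both reduce glucose/insulin levels and HOMA (homeostasis model assessment) score". Hypothesis 1 likewise expects a shift under both frequencies and adds that "A novel finding will be that LF is a powerful regulator of oxidative pathways in skeletal muscle". Hypothesis 3 speaks of participants as HF or LF subjects.

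**Design.** Allocation is described only as "Enrollment: Non-random assignment". The two arms are single-session exercise and long-term training. The second reads "Study Arm 2: Adaptations in gene regulation, metabolic markers, and subject-report metrics in response to up to 3 years of electrically induced exercise".

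**Methods, Study Arm 2.** Training refers back to the exercise description under Study Arm 1. That description covers electrode placement and the type of contraction but gives no frequency. HF and LF do not appear anywhere after the hypotheses.

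**Statistical Analysis Plan.** "Change over time for each outcome measure will be assessed via repeated-measures one-way ANOVA". The one contrast given for Arm 2 is post-training against baseline, for all outcomes. No group factor, group-by-time term or between-group test of change is given.

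**The concern.** Both Specific Aims are contrasts between two regimens, and the stated purpose concerns dose. The planned analysis has a single factor, time. Someone who follows the SAP exactly would finish without an estimate of the HF versus LF difference for any outcome.

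Two things are at stake. First, any HF versus LF statement in the report would rest on an analysis chosen after the fact, or on no analysis. Second, if participants on both frequencies are analysed together, a significant overall change could come from one frequency alone and still be reported as support for hypotheses that say both work, or for the LF-specific statement in Hypothesis 1.

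**Working it through.** The documents give no sample size, alpha, power, SD or HF/LF split, so there is no stated figure to reproduce. The finding rests on steps 1 and 2. Steps 3 and 4 use assumed inputs, for scale only.

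**1. What the test is.** Arm 2 has two time points. A repeated-measures one-way ANOVA with two levels is a paired t-test: F = t². On one simulated data set (n = 15), F = 1.784, t² = 1.784 and p = 0.203 for both.

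**2. What the test can see.** The paired t-test uses only the list of individual changes, and no frequency label enters. Take 12 invented changes: −1.4, −1.3, −1.2, −1.1, −1.0, −0.9, −0.3, −0.2, −0.1, 0, 0.1, 0.2. The mean is −0.60 and the SD 0.60, so t = −0.60/(0.60/√12) = −3.46, p = 0.005, under every labelling. The aims' quantity depends entirely on the labels:

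| Labelled HF | SAP test | HF minus LF (95% CI) |
|---|---|---|
| first six | t = −3.46 | −1.10 (−1.34 to −0.86) |
| last six | t = −3.46 | +1.10 (0.86 to 1.34) |
| every second value, from −1.3 | t = −3.46 | +0.10 (−0.71 to 0.91) |

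This holds for any sample size, effect or split.

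**3. If frequencies were pooled (illustration).** Assumptions: two-sided 5%, SD of change 1 in each group, n per group, mean change d in one frequency and 0 in the other, with d set so that the effective group alone has 80% power. For large n, d√n = 1.96 + 0.84 = 2.80. The pooled mean is d/2 on 2n participants, so its standardised value is (d/2)√(2n) = 2.80/√2 = 1.98. Power is 1 − Φ(1.96 − 1.98) = 0.51. Small samples give less, partly because the gap between the groups inflates the pooled SD. By simulation:

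| n per group | Pooled test significant |
|---|---|
| 5 | 0.40 |
| 8 | 0.451 |
| 10 | 0.465 |
| 30 | 0.494 |

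**4. Precision of the missing comparison (illustration).** Half-widths of 95% intervals in SDs of change, equal SDs, t on N − 2 df. At 10 per group t = 2.101:
- within one frequency: 2.101/√10 = 0.66
- HF minus LF: 2.101 × √(1/10 + 1/10) = 0.94

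At 20 per group the values are 0.45 and 0.64. With equal groups the ratio is √2 = 1.41.

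**The case against.** The strongest defence is that no hypothesis predicts a difference between HF and LF. Hypotheses 1 and 2 say that both work, Hypothesis 3 expects a trend in HF and LF subjects, and calling LF a powerful regulator is not a comparative claim. A baseline-to-post test within each frequency would fit all of these. The purpose can also be read as asking which dose produces a change.

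Much of that stands. A reader might infer that the paired test is a wrong choice, or that the hypotheses cannot be tested. The documents do not support either: run by frequency, the same test could address the hypotheses that say both. But the SAP does not say it is run by frequency. Two separate within-group results would also not be the comparison in the aims, since one significant and one non-significant result does not show a difference.

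It can also be said that a short SAP implies a group analysis. The test named has one factor, however, and the text says that factor is time.

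The illustrative figures rest wholly on assumptions: pooling, one inert frequency and a chosen power. That is right, and because no sample size is given, no single range covers every case. The finding does not need those figures.

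**Conclusion.** Wrong as written. The aims, the Arm 2 description and the SAP do not agree, and the planned analysis cannot make the comparison that both Specific Aims state. This follows from the text and from the algebra of a two-time-point test, with no assumption about sample size or effect.

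The size of any misreading is conditional. If frequencies are pooled with equal groups, one is inert and the other has 80% power on its own, the pooled test is significant about 40% of the time at 5 per group, 45% at 8, 47% at 10 and just under 50% at 30.

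Three further inferences go beyond the documents:
- **That HF and LF are pooled.** The SAP is silent on this.
- **That separate HF and LF groups do not exist.** Arm 2 does not identify them, but the aims and Hypothesis 3 suggest they were intended.
- **That allocation to HF or LF is known to be non-random.** The Design entry does not say what was assigned, and may mean only Arm 1 versus Arm 2.

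**What to change.** Reconcile the Study Objectives, the Study Arm 2 text and the SAP in one of two ways.

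**(A) Keep the comparison.** In the Arm 2 text, identify the HF and LF groups and how participants came to be in each. Analyse with group (HF, LF) between subjects and time (baseline, post-training) within subjects. For Aims 1 and 2 report the HF minus LF difference in change with a 95% CI, and report the change within each frequency with a 95% CI. Claim that both work only if each frequency shows the change in the hypothesised direction. Unless allocation to HF or LF was randomised, call it a non-randomised comparison and tabulate baseline values and actual training duration by group. Duration matters because the aims say 3 years and the Arm 2 text says up to 3 years.

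**(B) Give up the comparison.** If separate groups do not exist or are too small, reword Aims 1 and 2, Hypotheses 1 to 3 and the dose purpose as change over time, within frequency where applicable. State that no HF versus LF or dose-comparison conclusion will be drawn. Rewording the aims alone would leave the hypotheses and the purpose still naming or implying the two frequencies.

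**Cost.** Both are text edits; (A) also adds a group factor to the model. (A) needs a record of the frequency each participant received. Its between-frequency interval is wide at small sizes, and tabulating baseline values does not remove confounding. (B) costs nothing to run but loses the comparison. Naming one primary contrast per aim and adjusting for baseline are optional and not needed to cure the contradiction. No frequency, duration or regimen is proposed here.
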